# 9.3 Selection of Study Population

#### 9.3.1 Inclusion Criteria

Eligible subjects must meet/provide all of the following criteria:

- 1. Written informed consent.
- 2. Male or female between the ages of 18 and 80 years, inclusive, at Screening.
- 3. Meets the 2013 American College of Rheumatology/European League Against Rheumatism classification criteria for SSc with a total score of ≥9 [Van den Hoogen, 2013].
- 4. Classified as having skin involvement proximal to elbow, knee, face and neck, dcSSc subset [LeRoy and Medsger, 2001].
- 5. At the time of enrollment, no more than 60 months must have elapsed since the onset of the first dcSSc manifestations, other than Raynaud's phenomenon.
- 6. Skin thickening from dcSSc in the forearm suitable for repeat biopsy.
- 7. mRSS units  $\geq$ 10 and  $\leq$ 45 at Screening.
- 8. Subjects will be allowed to take CellCept® (mycophenolate mofetil) up to 3 g/day or Myfortic® (mycophenolic acid) up to 2.14 g/day and low-dose prednisone (≤10 mg/day or equivalent dosing of glucocorticoids). Subjects taking CellCept or Myfortic have been doing so for ≥20 weeks and the dose must have been stable for ≥16 weeks prior to the Day 1 Visit. Prednisone must have been at a stable dose for ≥4 weeks prior to the Day 1 Visit.
- 9. Diabetic subjects must have HbA1c ≤8.0%, with no new diabetic medication (oral or insulin) or more than a 10% change in the dose of a currently prescribed diabetic medication within 60 days prior to Screening.
- 10. Women of childbearing potential (including those with an onset of menopause <2 years prior to Screening, nontherapy-induced amenorrhea for <12 months prior to Screening or not surgically sterile [absence of ovaries and/or uterus]) must have a negative serum pregnancy test at Screening and negative urine pregnancy tests at all protocol-specified timepoints (i.e., prior to each dose and throughout the subject's participation in the Follow-up Period); subjects who are sexually active with a non-vasectomized male partner must agree to use 2 reliable forms of contraception during the trial, one of which is recommended to be hormonal, such as an oral contraceptive. Hormonal contraception must be started at least 1 full cycle prior to Baseline and continue for 180 days after the last dose of study drug. Highly effective contraceptive methods (with a failure rate <1% per year), when used consistently and correctly, include implants, injectables, combined oral contraceptives, some intrauterine devices, sexual abstinence or vasectomized partner.

11. Willing and able to comply with the prescribed treatment protocol and evaluations for the duration of the study.

#### 9.3.2 Exclusion Criteria

Subjects will be ineligible for study participation if they meet any of the following criteria:

- 1. Diagnosed with limited cutaneous SSc or sine scleroderma.
- 2. Diagnosed with other autoimmune connective tissue diseases except for fibromyalgia, scleroderma-associated myopathy and Sjogren's syndrome.
- 3. Scleroderma renal crisis diagnosed within 6 months of the Screening Visit, characterized by abrupt onset of hypertension and acute kidney injury (see Section 9.5.1.1).
- 4. FVC <50% predicted, diffusing capacity of the lungs for carbon monoxide (DLCO) <40% predicted or PAH by right heart catheterization requiring treatment with more than one oral PAH-approved therapy or parenteral therapy (intermittent use of phosphodiesterase-5 inhibitors are allowed for erectile dysfunction and/or Raynaud's phenomenon/digital ulcers).
- 5. Corticosteroid use for conditions other than dcSSc within 4 weeks prior to Screening (topical steroids for dermatological conditions and inhaled steroids are allowed).
- 6. Previous treatment with rituximab (Rituxan® or MabThera®) within 12 months prior to the first infusion.
- 7. Use of a non-steroidal immunosuppressive agent, cytotoxic or anti-fibrotic drug within 4 weeks of Screening, including cyclophosphamide, azathioprine (Imuran®), methotrexate or other immunosuppressive or cytotoxic medication. Exceptions are mycophenolate mofetil (CellCept) and mycophenolic acid (Myfortic), which are permitted according to inclusion criterion 8, and anti-malarials (e.g., hydroxychloroquine [Plaquenil®]).
- 8. Use of biologics or small molecules approved for rheumatoid arthritis, psoriatic arthritis and other rheumatic diseases within 4 weeks prior to Screening.
- 9. Use of an investigational agent for any condition within 90 days or 5 half-lives, whichever is longer, prior to Screening or anticipated use during the course of the trial.
- 10. Malignant condition in the past 5 years (except successfully treated basal/squamous cell carcinoma of the skin or cervical cancer in situ).
- 11. Pregnant or lactating women.
- 12. Current drug or alcohol abuse or history of either within the previous 2 years, in the opinion of the Investigator or as reported by the subject.
- 13. Biopsy-proven or clinically suspected IBD (e.g., diarrhea with or without blood or rectal bleeding associated with abdominal pain or cramping/colic, urgency, tenesmus or incontinence for more than 4 weeks without a confirmed alternative diagnosis OR

Date: 02 February 2022

IND 147532

TEPEZZA (HZN-001) Protocol: HZNP-TEP-001 Version 5.0, Amendment 4

endoscopic or radiologic evidence of enteritis/colitis without a confirmed alternative diagnosis).

- 14. Known hypersensitivity to any of the components of TEPEZZA or prior hypersensitivity reactions to mAbs.
- 15. Previous enrollment in this study or participation in a prior teprotumumab-trbw clinical trial.
- 16. Human immunodeficiency virus, untreated or positive viral load for hepatitis C or hepatitis B infections.
- 17. Previous organ transplant (including allogeneic and autologous marrow transplant).
- 18. Alanine aminotransferase or aspartate aminotransferase >2.5 times the upper limit of normal or estimated glomerular filtration rate of <30 mL/min/1.73m^2 at Screening.
- 19. Platelets  $<100\times10^3/\mu$ L.
- 20. Hemoglobin <8 g/dL.
- 21. Any other condition that, in the opinion of the Investigator, would preclude inclusion in the study.

# 9.3.3 Removal of Subjects from Treatment or the Study

All subjects are free to withdraw from study participation at any time, for any reason and without prejudice to their further medical care. Subjects who prematurely discontinue study drug during the Treatment Period will be encouraged to continue study participation, particularly returning for the Week 24 (end of treatment) assessments, and continue in the 24-week Follow-up Period. Subjects who discontinue study drug due to an AE should be followed until resolution or stabilization of the AE, or an adequate explanation for the event is obtained.

If further participation in the study is not in the best interest of the subject, the Investigator may terminate a subject from treatment or from the study.

#### 9.3.3.1 Removal of Subjects from Treatment

The primary reason for discontinuation from study drug should be recorded on the eCRF using one of the following categories:

- Adverse event. The subject experiences an AE that imposes an unacceptable risk to the subject's health, or the subject is unwilling to continue receiving treatment because of an AE. Subjects who discontinue study drug due to an AE will remain in the study unless they withdraw from the study for another reason. AEs requiring permanent study drug discontinuation per the protocol include:
  - o A drug-related anaphylactic reaction.
  - Severe drug-related hyperglycemia (e.g., blood glucose >250 mg/dL) that does not abate to mild or moderate intensity with anti-diabetic treatment (dose may be skipped up to 2 times prior to permanently discontinuing study drug; see Section 9.4.6.3.2 for details).

Date: 02 February 2022

IND 147532

TEPEZZA (HZN-001) Protocol: HZNP-TEP-001 Version 5.0, Amendment 4

- Diagnosed or suspected IBD (e.g., diarrhea with or without blood or rectal bleeding associated with abdominal pain or cramping/colic, urgency, tenesmus or incontinence for more than 4 weeks without a confirmed alternative diagnosis OR endoscopic or radiologic evidence of enteritis/colitis without a confirmed alternative diagnosis).
- Lack of efficacy. Discontinuation of study drug due to lack of efficacy is at the discretion of the Investigator or subject and may occur if the Investigator determines that study drug administration is not benefitting the subject. Subjects who discontinue study drug due to lack of efficacy will remain in the study unless they withdraw from the study for another reason.
- Withdrawal by subject/guardian. The subject wishes to withdraw from study treatment. The clinical site should attempt to determine the underlying reason for the voluntary withdrawal and document it on the eCRF.
- Study terminated by Sponsor. The Sponsor, IRB/IEC or regulatory agency terminates the study.
- Pregnancy.
- Death.
- Completed. The subject completed treatment.

## 9.3.3.2 Removal of Subjects from the Study

The primary reason for discontinuation from the study should be recorded on the eCRF using one of the following categories:

- Lost to follow-up. The subject does not return to the clinic for scheduled assessments and does not respond to the site's attempts to contact the subject.
- Withdrawal by subject/guardian. The subject wishes to withdraw from the study. The clinical site should attempt to determine the underlying reason for the voluntary withdrawal and document it on the eCRF.
- Death.
- Completed. The subject completed the study.

If a subject prematurely discontinues from the study during the Follow-up Period, he/she will return for a clinic visit and undergo the Week 48 (end of study) assessments.

# 9.3.4 Replacement Policy

#### **9.3.4.1** Subjects

In general, no subject prematurely discontinued from the study for any reason will be replaced. An exception may be made for subjects who are unevaluable due to the impact of an event, for example, a pandemic or a natural disaster, and associated restrictions on movement and work.

TEPEZZA (HZN-001) Protocol: HZNP-TEP-001 Version 5.0, Amendment 4

Subjects unable to receive treatment or be evaluated due to restrictions during the event may be replaced, at the discretion of the Sponsor. This may result in more subjects being enrolled into the study to allow for the planned number to be evaluable for the efficacy and safety analyses.

### 9.3.4.2 Centers

A center may be closed and/or replaced for the following administrative reasons:

- Excessively slow recruitment.
- Poor protocol adherence.

## 9.3.4.3 Screen Failures

Subjects who do not meet all of the inclusion criteria or meet any of the exclusion criteria will be considered screen failures. Screen failures may be allowed to rescreen for the study if both the Investigator and Sponsor are in agreement regarding rescreening and if the Investigator determines that the subject can satisfy all of the eligibility criteria.

#### 9.4 Treatments

#### 9.4.1 Treatments Administered

All study drug dosing will be performed at the clinic or infusion center under the supervision of clinic staff or nurses. On Day 1 of the double-blind Treatment Period, subjects will be randomized in a 3:2 ratio to receive infusions of either:

- 1. TEPEZZA (10 mg/kg on Day 1 followed by 20 mg/kg q3W for the remaining 7 infusions), or
- 2. Placebo (q3W for all 8 infusions).

The infusion rate may be reduced and the dose may be interrupted or held based on tolerability. The first and second infusions will be administered over approximately 90 minutes (but not less than 80 minutes). Subsequent infusions will be administered over approximately 60 minutes (but not less than 50 minutes), providing there are no significant infusion-associated events.

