- 13. Biopsy-proven or clinically suspected inflammatory bowel disease (e.g., diarrhea with or without blood or rectal bleeding associated with abdominal pain or cramping/colic, urgency, tenesmus or incontinence for more than 4 weeks without a confirmed alternative diagnosis OR endoscopic or radiologic evidence of enteritis/colitis without a confirmed alternative diagnosis).
- Known hypersensitivity to any of the components of TEPEZZA or prior hypersensitivity reactions to mAbs.
- 15. Previous enrollment in this study or participation in a prior teprotumumab-trbw clinical study.
- Human immunodeficiency virus, untreated or positive viral load for hepatitis C or hepatitis B infections.
- 17. Previous organ transplant (including allogeneic and autologous marrow transplant).
- 18. Alanine aminotransferase or aspartate aminotransferase >2.5 times the upper limit of normal or estimated glomerular filtration rate of <30 mL/min/1.73m^2 at Screening.
- 19. Platelets  $<100\times10^3/\mu L$ .
- 20. Hemoglobin <8 g/dL.
- 21. Any other condition that, in the opinion of the Investigator, would preclude inclusion in the study.

Date: 02 February 2022 IND 147532

Dose Regimen/Route of Administration:

All study drug dosing will be performed at the clinic or infusion center under the supervision of clinic staff or nurses. On Day 1 of the double-blind Treatment Period, subjects will be randomized in a 3:2 ratio to receive infusions of either:

- 1. TEPEZZA (10 mg/kg on Day 1 followed by 20 mg/kg q3W for the remaining 7 infusions),
- 2. Placebo (q3W for all 8 infusions).

The infusion rate may be reduced and the dose may be interrupted or held based on tolerability (see Section 9.4.6.3.2 for details). The first and second infusions will be administered over approximately 90 minutes (but not less than 80 minutes). Subsequent infusions will be administered over approximately 60 minutes (but not less than 50 minutes), providing there are no significant infusion-associated events.

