#### 9.4.6.3 Details Concerning Timing and Dose Administration

#### 9.4.6.3.1 Preparation and Administration of TEPEZZA

TEPEZZA will be prepared by the site pharmacist (or designee in accordance with institutional policies and local regulations), who is not blinded to the identity of the study medication. Each vial of TEPEZZA will be reconstituted with 10 mL of sterile water for injection. The resulting solution will have a concentration of 47.6 mg/mL teprotumumab-trbw antibody. Reconstituted TEPEZZA solution will be further diluted in 0.9% (w/v) NaCl solution prior to administration by the site pharmacist or designee.

Doses up to 1800 mg will be administered in a total infusion volume of 100 mL and those above 1800 mg will be administered in a total infusion volume of 250 mL. To maintain a constant volume in the infusion bags, a volume equal to the volume of TEPEZZA to be placed into the infusion bag will first be removed from the infusion bag using a sterile syringe and needle. The appropriate volume of reconstituted drug product solution based on the subject's dose and body weight will be withdrawn and the TEPEZZA drug product solution will be diluted with normal saline (0.9% NaCl) in the infusion bag. Dosing on Day 1 and at Weeks 3, 6 and 9 during the double-blind Treatment Period will be based on the weight measured on Day 1. Dosing at

Date: 02 February 2022

IND 147532

TEPEZZA (HZN-001) Protocol: HZNP-TEP-001 Version 5.0, Amendment 4

Weeks 12, 15, 18 and 21 during the double-blind Treatment Period will be based on the weight measured at Week 9.

The infusion is to be administered at room temperature (20°C to 25°C [68°F to 77°F]).

The storage time of reconstituted TEPEZZA solution in the vial and the diluted solution in the infusion bag are outlined in the most recent version of the Investigator's Brochure and in the Investigational Pharmacy Manual provided to the site. If refrigerated prior to administration, allow the diluted solution to reach room temperature prior to infusion.

No incompatibilities between TEPEZZA and polyethylene, polyvinyl chloride, polyurethane or polyolefin bags and IV administration sets have been observed. Exposure of the solution to direct sunlight should be avoided.

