Parenteral drug products should be inspected visually for particulate matter and discoloration prior to administration, whenever solution and container permit. Upon reconstitution, TEPEZZA is a colorless or slightly brown, clear to opalescent solution which is free of foreign particulate matter. Discard the solution if any particulate matter or discoloration are observed.

Do not freeze the reconstituted or diluted solution.

Partially used vials should not be re-used.

The first and second IV infusions on Day 1 and Week 3 will be administered over approximately 90 minutes (but not less than 80 minutes) for all subjects; subsequent infusions may be administered over a shorter time period (approximately 60 minutes, but not less than 50 minutes) in the absence of any infusion-associated events. All subjects will be monitored for AEs from the start of infusion through 60 minutes after infusion completion for the first 3 doses; the monitoring period for subsequent doses may be reduced to 30 minutes after infusion completion for subjects who do not experience infusion-associated events.

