## 9.4.6.3.2 Dose Modifications, Interruptions and Delays

All dosing instructions are applicable for TEPEZZA and placebo administration.

Subjects will be monitored for immediate infusion-associated events (e.g., facial flushing, warmth, dyspnea, dizziness, hypertension, hypotension, pruritus) and delayed infusion-associated events (e.g., rash). If immediate infusion-associated events are noted, the infusion rate will be slowed or interrupted, symptomatic treatment (e.g., antipyretics, antihistamines, beta-agonists, oxygen, IV fluid) may be administered and vital signs (temperature, blood pressure, pulse and respiratory rate) will be monitored every 5 minutes until stable and then every 15 minutes for 2 additional determinations. The infusion may be restarted upon complete resolution of symptoms; however, study drug dosing will be permanently discontinued if the event is an anaphylactic reaction.

Date: 02 February 2022 IND 147532

TEPEZZA (HZN-001) Protocol: HZNP-TEP-001 Version 5.0, Amendment 4

Following the appearance of either immediate or delayed infusion-associated events, subsequent doses may be pre-treated with diphenhydramine (1 to 1.25 mg/kg IV; maximum of 50 mg), ranitidine (50 mg IV), famotidine (0.5 mg/kg IV), dexamethasone (0.4 mg/kg IV; maximum of 20 mg) and/or acetaminophen (500 mg). All subsequent infusions will be administered over approximately 90 minutes (but not less than 80 minutes) with vital signs monitored every 15 minutes from the start of the infusion through 60 minutes after infusion completion.

If delayed infusion-associated events are noted, subjects may continue dosing at the Investigator's discretion; however, if a rash worsens following repeated dosing or other signs of serum sickness (e.g., delayed fever, myalgias, arthralgias) are present, study drug dosing will be permanently discontinued.

In general, the decision to continue dosing should take into consideration the potential benefit and risk to a subject.

In the event a subject's HbA1c level rises to >8% while in the study, the Investigator must determine the risk versus benefit for each subject to remain in the study.

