## 9.5.7.4 Vital Signs, Weight and Height

Vital signs (heart rate, blood pressure, respiratory rate, temperature) will be measured at all clinic visits. Vital signs will be measured pre- and post-infusion on Day 1 and Week 3 and pre-infusion on all other dosing days. In addition, if immediate infusion-associated events are noted during the infusion, vital signs will be monitored every 5 minutes until stable and then every 15 minutes for 2 additional determinations. Also, vital signs will be monitored every 15 minutes from the start of the infusion through 60 minutes after infusion completion for any subsequent infusions after the previous occurrence of immediate or delayed infusion-associated events.

Blood pressure and pulse measurements will be obtained with the subject's arm unconstrained by clothing or other material and while the subject is sitting up. When possible, the same arm will be used for measurements in all study visits.

Weight will be measured at Screening and on Day 1, Weeks 3, 6, 9, 12, 15, 18, 21, 24, 36 and 48. To limit the potential for variability in weight collection, the subject should wear lightweight

Horizon Therapeutics U.S.A., Inc. Date: 02 February 2022

IND 147532

TEPEZZA (HZN-001) Protocol: HZNP-TEP-001 Version 5.0, Amendment 4

clothing and no shoes during weighing. Dosing on Day 1 and at Weeks 3, 6 and 9 during the double-blind Treatment Period will be based on the weight measured on Day 1. Dosing at Weeks 12, 15, 18 and 21 during the double-blind Treatment Period will be based on the weight measured at Week 9.

Height will be measured at Screening only.

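### For a subject with a non-significant infusion-associated event, the synopsis and Section 9.4.1 default to about 60-minute infusions, while Section 9.4.6.3 calls for about 90 minutes

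*Protocol*

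**What the plan says.** Four places in the current protocol set the duration of the third and later infusions, and a fifth sets the matching monitoring.

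- **Section 9.4.1 (Treatments Administered):** "Subsequent infusions will be administered over approximately 60 minutes (but not less than 50 minutes), providing there are no significant infusion-associated events". The paragraph opens by allowing the infusion to be slowed, interrupted or held according to tolerability.
- **Synopsis (Dose Regimen/Route of Administration):** the same duration and condition, "providing there are no significant infusion-associated events". A cross-reference to Section 9.4.6.3.2 is attached to the preceding tolerability sentence.
- **Section 9.4.6.3.1 (Preparation and Administration):** the shorter time is optional and available only "in the absence of any infusion-associated events".
- **Section 9.4.6.3.2 (Dose Modifications, Interruptions and Delays):** the paragraph begins "Following the appearance of either immediate or delayed infusion-associated events, subsequent doses may be pre-treated" and goes on: "All subsequent infusions will be administered over approximately 90 minutes (but not less than 80 minutes". It also requires vital signs every 15 minutes during those infusions and for 60 minutes afterwards.
- **Section 9.5.7.4 (Vital Signs):** the same 15-minute monitoring applies "for any subsequent infusions after the previous occurrence of immediate or delayed infusion-associated events".

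No definition of a significant infusion-associated event appears in the supplied text. Section 9.4.6.3.2 gives facial flushing, warmth and pruritus among its examples of immediate events.

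**The concern.** Two sections make the short infusion the default unless an event passes an undefined threshold. Two others withdraw it after an event of any kind. The wording that sets the duration is directive both in 9.4.1 and in 9.4.6.3.2.

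Infusion reaction is an adverse event of special interest (Sections 7.1.3.4.4.4 and 9.5.7.1.1.5) and part of the safety endpoint in Section 9.6.1.5. A subject who has had a mild reaction could be re-exposed faster than 9.4.6.3.2 allows by a site following 9.4.1. Section 9.7 requires every protocol deviation to be documented, yet whether that infusion is a deviation depends on the section used to judge it. The dosing instructions apply to both arms, so the question arises for any randomized subject with an event.

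**Working it through.** No power, sample size or event-count figure is involved, so there is no figure in the plan to reproduce. The check is a comparison of the rules, followed by simple rate arithmetic.

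**Step 1. Apply each rule to each kind of subject (third infusion onward).**

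| Subject's history | Synopsis and 9.4.1 | 9.4.6.3.1 | 9.4.6.3.2 |
|---|---|---|---|
| No event | about 60 min, minimum 50 | about 60 min allowed | post-event rule not triggered |
| Significant event | 60-min default lost | shorter time not available | about 90 min, minimum 80 |
| Event judged not significant | about 60 min, minimum 50 | shorter time not available | about 90 min, minimum 80 |

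The rules are compatible in the first two rows. They diverge only in the third.

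**Step 2. Does 9.4.6.3.2 carry a hidden severity threshold?** Its paragraph is triggered by either kind of event, with no grade attached. Section 9.5.7.4 restates the paired monitoring rule with the same trigger and no threshold. The detailed sections are therefore consistent with each other.

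**Step 3. Can one infusion satisfy every section in the third row?**

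- A 60-minute infusion meets 9.4.1 but is below the 80-minute minimum in 9.4.6.3.2 (60 < 80), so it fails.
- A 90-minute infusion meets 9.4.6.3.2 and 9.4.6.3.1, and is permitted by 9.4.1 through its tolerability clause. It passes, but 9.4.1 does not direct the site to it.

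**Step 4. Size of the difference.** Rate = infusion volume / duration. Section 9.4.6.3.1 fixes the volume: "Doses up to 1800 mg will be administered in a total infusion volume of 100 mL and those above 1800 mg" in 250 mL.

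- 100 mL: 100/60 = 1.67 mL/min against 100/90 = 1.11 mL/min.
- 250 mL: 250/60 = 4.17 mL/min against 250/90 = 2.78 mL/min.
- Ratio at the nominal times: 90/60 = 1.5. Ratio at the stated minimum times: 80/50 = 1.6.

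The ratio does not depend on body weight. The documents give no typical weight. For assumed weights of 60, 80 and 100 kg at 20 mg/kg:

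- 60 kg: 1200 mg; 1200/60 = 20.0 against 1200/90 = 13.3 mg/min.
- 80 kg: 1600 mg; 1600/60 = 26.7 against 1600/90 = 17.8 mg/min.
- 100 kg: 2000 mg; 2000/60 = 33.3 against 2000/90 = 22.2 mg/min.

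**Step 5. Number of infusions affected.** Infusions 1 and 2 run over about 90 minutes for everyone. A first event at infusion 1 or 2 leaves infusions 3 to 8 in question, which is 6. A first event at a later infusion k leaves 8 − k. Six is therefore a ceiling.

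**The case against.** The strongest reply is that a site is not forced into a breach. A reader might infer that the two directive rules cannot both be followed. The documents do not support that: the tolerability clause in the synopsis and 9.4.1 lets a site run 90 minutes, and Step 3 shows that this satisfies every section. The synopsis also points to 9.4.6.3.2, as do the study design descriptions in the synopsis and Section 9.1, and a site that follows the pointer finds a single trigger there.

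This weakens the conflict without removing it. The clause is permissive where 9.4.6.3.2 is directive. The cross-references are attached to that clause, not to the 60-minute condition, and 9.4.1 has none. No supplied text says that the detailed section prevails.

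Two other inferences also go too far.

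- A reader might treat infusion rate as the main protection against recurrence. Section 9.4.6.3.2 also provides for symptomatic treatment, pre-treatment and closer monitoring. The one subject in the thyroid eye disease program who continued after a reaction had both pre-medication and a slower rate, so nothing can be credited to rate alone.
- A reader might say that recurrence could not be interpreted across sites. Start and stop times are recorded for each infusion (Section 9.4.10) and rate adjustments are to be reported (Section 9.4.6.3.2), so the actual durations would be known. No recurrence analysis is planned.

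Numbers would also be small. Section 7.1.3.4.4 reports 3 adjudicated infusion-related reactions and 121 exposed subjects: 3/121 = 2.5%. If that rate held here, 15 treated subjects would give 15 × 3/121 = 0.4 expected, and a chance of at least one of 1 − (118/121)^15 = 31%. Those reactions were adjudicated by the sponsor. Milder events may be more frequent, and the documents give no rate for them.

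**Conclusion.** The inconsistency is real and lies in the current text. It concerns only events that a site judges not significant. For those, the default durations differ by a factor of 1.5 in rate (1.6 at the minimum times), for at most six infusions per subject, and a 60-minute infusion accepted under 9.4.1 would be short of the 9.4.6.3.2 minimum.

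It is a wording conflict in a safety rule for an event of special interest, and it does not touch the primary analysis. The consequences that the documents support are possible faster re-exposure after a mild reaction and an unclear standard for calling a deviation.

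The practical effect is limited. SAP Sections 1 and 3 report early termination with 3 subjects enrolled, and Sections 6 and 7 replace all analysis with listings. The supplied documents do not say whether any of the three had an infusion event. Protocol deviation and safety listings remain planned, so a single standard would still be needed if one did.

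The conclusion assumes that the undefined threshold excludes some mild events and that no definition exists outside the supplied text, for example in a pharmacy manual.

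**What to change.** Reconcile the synopsis, Section 9.4.1, Section 9.4.6.3.1 and Section 9.4.6.3.2 so that one trigger, in the same words, governs the duration of later infusions, and keep Section 9.5.7.4 consistent with it. If the trigger depends on an event being significant, define the term. The sponsor decides which trigger applies; this review takes no view on the duration or threshold.

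For the abbreviated report, state which rule was used to classify any infusion given after an event in the deviation listing.

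The cost is wording in an amendment and in the pharmacy and infusion instructions, or a sentence in the report now that the study has stopped. It needs no extra data, visits or analyses.
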